8.1.3. Exploratory Efficacy Analyses

8.1.3.1. Overview of Planned Exploratory Efficacy Analyses

Table 8 provides an overview of the planned exploratory efficacy analyses.

Table 8 Overview of Planned Exploratory Efficacy Analyses

Endpoint	Analysis		Abse	olute	Cha	om Base	Baseline		
-	Population	Sum	Summary Individual		Summary I		Indiv	ndividual	
		Т	F	F	L	Т	F	F	L
Hgb Variability									
Hgb observed (including imputed) and change from baseline (CFB) at all visits	ITT	Include	ed with H	gb co-priı	mary and 7.1)	suppor	tive anal	lyses (Se	ection
% of time Hgb is above, within and below Hgb analysis range during EP and MP	ITT	In	cluded w	ith Hgb s	econdary	analyse	es (Secti	ion 8.1.2	2)
Number (%) of subjects with mean Hgb above, within and below Hgb analysis range during EP and at the end of treatment	ITT	In	cluded w	ith Hgb s	econdary	analyse	es (Secti	ion 8.1.2)

200807

Endpoint	Analysis		Abs	olute	Change from Baseline					
	Population	Sum	imary	Summary Individ						
		Т	F	F	vidual L	T	F	F	L	
Number (%) of subjects with Hgb < 7.5 g/dL during EP and MP ¹	ITT	Y								
Number of times Hgb < 7.5 g/dL during EP and MP ¹	ITT	Y								
Number (%) of subjects with a >1g/dL increase in Hgb over 2 weeks (assessed at Week 2 and Week 4) or a >2 g/dL increase in Hgb within any 4 week period from Week 4 to Week 52 ¹	ITT	Y								
Number (%) of subjects with a >1g/dL decrease in Hgb over 2 weeks (assessed at Week 2 and Week 4) or a >2 g/dL decrease in Hgb within any 4 week period from Week 4 to Week 52 ¹	ITT	Y								
N (%) of subjects with a Hgb value ≥ 12 g/dL during the EP and MP ¹	ITT	Y								
Number of times Hgb \geq 12 g/dL during the EP and MP ¹	ITT	Y								
% of time Hgb \ge 12 g/dL during the EP and MP ¹	ITT	Y								
Iron Parameters										
Hepcidin, ferritin, TSAT, total iron, TIBC observed and CFB at all visits	ITT	Y	Y			Y	Y			
Average quarterly IV iron dose/subject	ITT	Y	Y							
Average quarterly TSAT	ITT	Y	Y							
Average quarterly ferritin	ITT	Y	Y							
Subjects who met iron management criteria	ITT	Y								
Subjects who reduced IV iron during EP	ITT	Y								

200807

Endpoint	Analysis		Abs	olute	Change from Baseline				
	Population	Sum	imary	Indiv	vidual		mary		ridual
	-	Т	F	F	L	Т	F	F	L
relative to Baseline									
RBC and Whole Blood	Transfusions	•			•				
Number (%) of subjects									
receiving at least one									
RBC or whole blood	ITT	Y							
transfusion by Week 52									
and by end of treatment									
Number of RBC and									
whole blood transfusion	ITT	Y							
events per 100 patient									
years									
Number of RBC and									
whole blood	ITT	Y							
transfusions per 100									
patient years									
Number of RBC and									
whole blood units per	ITT	Y							
100 patient years									
Time to first RBC or	ITT	Y	Y						
whole blood transfusion									
DGF	1	1	1	1		1	1	1	1
Number (%) of subjects	ITT	Y							
experiencing DGF	177	Y							
Duration of DGF		ľ							
Dose Adjustment Sche		Y		1			1	1	r
Assigned dose by visit	ITT	ř	Y						
Most recent dose by	ITT		Y						Y
visit									
Number (%) of patients with 0,1,2, 10, or >10									
dose adjustments									
during the following									
periods: Day 1 - <week< td="">ITT	Y								</week<>	ITT	Y							
28, Week 28 – <week< td="">									</week<>									
52, Day 1 – < end of									
treatment									
Number of dose									1
adjustments during the									
following periods: Day 1	177	v							
- <week -<="" 28="" 28,="" td="" week="">ITT	Y								</week>	ITT	Y							
<week 1="" 52,="" <<="" day="" td="" –="">									</week>									
end of treatment									
Time dose held for Hgb	ITT	Y							
≥ 12 g/dL									
Dosing algorithm	ITT	Y2	Y2						
update ¹	111	[-	1-						

200807

NOTES:

- T = Table, F = Figure, L = Listing, Y = Yes display generated.
- Summary = Represents TFL related to any summaries (i.e. descriptive statistics) of the observed raw data.
- Individual = Represents FL related to any displays of individual subject observed raw data.
- ^[1] Summaries will be presented using evaluable Hgb values only (see Section 10.6.3).

^[2] Summary tables and figures will contain the results of a statistical model.

8.1.3.2. Planned Exploratory Efficacy Display Details

Hgb Variability

The number and percentage of subjects with a Hgb value < 7.5g/dL and the number of times a Hgb value < 7.5 g/dL occurs during the EP and the MP will be summarized by treatment group using central laboratory Hgb values and separately using HemoCue Hgb values. This summary will be presented using evaluable Hgb values only (see Section 10.6.3). The central laboratory summary will be considered the primary summary of this data.

The number and percentage of subjects with a >1 g/dL increase in Hgb over 2 weeks (assessed at Week 2 and Week 4) or a >2 g/dL increase in Hgb within any 4-week period from Week 4 to Week 52 will be summarized by visit and overall at Week 52 by treatment group using HemoCue Hgb values. This summary will be presented using evaluable Hgb values only (see Section 10.6.3).

The number and percentage of subjects with a >2 g/dL increase in Hgb within any 4week period from Week 4 to Week 52 will be summarized by visit and overall at Week 52 by treatment group using central laboratory Hgb values. This summary will be presented using evaluable Hgb values only (see Section 10.6.3). The central laboratory summary will be considered the primary summary of this data.

The number and percentage of subjects with a >1 g/dL decrease in Hgb over 2 weeks (assessed at Week 2 and Week 4) or a >2 g/dL increase in Hgb within any 4-week period from Week 4 to Week 52 will be summarized by visit and overall at Week 52 by treatment group using HemoCue Hgb values. This summary will be presented using evaluable Hgb values only (see Section 10.6.3).

The number and percentage of subjects with a >2 g/dL decrease in Hgb within any 4week period from Week 4 to Week 52 will be summarized by visit and overall at Week 52 by treatment group using central laboratory Hgb values. This summary will be presented using evaluable Hgb values only (see Section 10.6.3). The central laboratory summary will be considered the primary summary of this data.

The number and percentage of subjects with a Hgb value ≥ 12 g/dL and the number of times a Hgb value ≥ 12 g/dL occurs during the EP and the MP will be summarized by treatment group using central laboratory Hgb values and separately using HemoCue Hgb values. This summary will be presented using evaluable Hgb values only (see Section 10.6.3). The central laboratory summary will be considered the primary summary of this data.

The percentage of time Hgb is ≥ 12 g/dL and the percentage of time Hgb is ≥ 12 g/dL for subjects with at least one Hgb ≥ 12 g/dL during the MP and the EP will be calculated using the Rosendaal method as described in Section 8.1.2. The percentage of time Hgb is ≥ 12 g/dL during the MP and the EP will be summarized using mean, standard deviation, minimum, P25, median, P75, and maximum by treatment group. This summary will be presented using evaluable Hgb values only (see Section 10.6.3).

Iron Parameters

Hepcidin, ferritin, and total iron on-treatment values will be log-transformed (see Section 10.5.2) and summarized using geometric mean, coefficient of variation, minimum, P25, median, P75, and maximum for each scheduled visit by treatment group. Graphical summaries will be provided.

TSAT and TIBC on-treatment values will be summarized using mean, standard deviation, minimum, P25, median, P75, and maximum for each scheduled visit by treatment group. Graphical summaries will be provided.

Percent change from baseline in log-transformed (see Section 10.5.2) hepcidin, ferritin, and total iron on-treatment values will be summarized using geometric mean, 95% confidence interval, minimum, P25, median, P75, and maximum for each scheduled visit by treatment group. Graphical summaries will be provided.

Change from baseline in TSAT and TIBC on-treatment values will be summarized using mean, standard deviation, minimum, P25, median, P75, and maximum for each scheduled visit by treatment group. Graphical summaries will be provided.

Average quarterly IV iron dose/subject while on treatment will be summarized by presenting average monthly IV iron dose by quarter (see Section 10.6.3). Summaries will include mean, standard deviation, minimum, P25, median, P75, and maximum by treatment group. Graphical summaries will be provided.

Average quarterly TSAT while on treatment will be summarized by presenting average TSAT values for the quarters used to generate IV iron dose by quarter (see Section 10.6.3). Summaries will include mean, standard deviation, minimum, P25, median, P75, and maximum by treatment group. Graphical summaries will be provided.

Average quarterly ferritin while on treatment will be summarized by presenting average ferritin values by quarter (see Section 10.6.3). Summaries will include geometric mean, coefficient of variation, minimum, P25, median, P75, and maximum by treatment group. Graphical summaries will be provided.

The number and percentage of subjects that met the iron management criteria during the study while on treatment will be summarized by treatment group for each 3-month period of the study, the first year and across the entire study. There are two types of iron management thresholds: the first type requires that iron therapy be administered if subjects have ferritin and/or TSAT values that are too low; the second type requires that all iron (excluding multivitamins) must be stopped if ferritin and/or TSAT values are too high. It is also possible for a subject to meet starting and stopping criteria on the same

200807

day with a low ferritin and a high TSAT. These subjects will also be summarized (see Section 10.6.3). Assessment of meeting iron management thresholds will be made based on central laboratory data values at the scheduled visits for ferritin and TSAT assessments, according to the schedule outlined in the Time and Events table (see Section 10.2.1). Further, the subjects who met the threshold requiring iron administration to start or stop while on IV iron will be grouped by the action taken with IV iron therapy in the 8 weeks following the date the threshold was met (i.e., starting or increasing iron therapy, maintaining existing iron therapy, receiving no iron therapy, stopping or decreasing iron therapy with no increase, Section 10.6.3) according to concomitant medication records for IV iron.

The number and percentage of subjects that reduced IV iron supplementation relative to baseline during the EP while on treatment will be summarized by treatment group (see Section 10.6.3).

RBC and Whole Blood Transfusions

Summary and analysis tables will use the ITT population.

The total number of on-treatment RBC and whole blood transfusion events, transfusions and units for each subject will be derived as described in Section 10.6.3.

The number of on-treatment RBC and whole blood transfusion events per subject, the number of subjects with at least one RBC and whole blood transfusion event, and total number of RBC and whole blood transfusion events will be summarized.

The number of on-treatment RBC and whole blood transfusions events per 100 patient years will be summarized by treatment group.

The number of on-treatment RBC and whole blood transfusions per 100 patient years will be summarized by treatment group.

The number of on-treatment RBC and whole blood units per 100 patient years will be summarized by treatment group.

The reason for transfusion events will be summarized.

The above summaries will be produced for the Evaluation Period, Week 52 and End of Treatment.

An analysis of time to first RBC or whole blood transfusion will be performed as described in Section 10.6.3, including a Kaplan-Meier plot.

All transfusion summaries will be repeated for the primary definition of ESA hyporesponder subgroups (see Section 10.6.2).

DGF

Delayed graft function after deceased donor kidney transplantation is defined in Section 10.6.3.

200807

The number and percentage of patients experiencing DGF after deceased donor kidney transplantation will be summarized by treatment group.

The length of time in days that subjects experience DGF after deceased donor kidney transplantation will be summarized using mean, standard deviation, minimum, P25, median, P75, and maximum by treatment group.

Dose Adjustment Scheme

See Section 10.6.3 for additional details of dose adjustment scheme endpoints.

For exploratory summaries of dose levels, subjects in the rhEPO arm will be further divided into subjects receiving epoetin alfa and subjects receiving darbepoetin alfa. The total weekly dose of epoetin alfa will be summarized and the total 4-weekly dose of darbepoetin alfa will be summarized (see Section 10.6.3). Since it is possible for subjects to switch from epoetin alfa to darbepoetin alfa during the study, subjects who receive both treatments during the study will be counted in each group.

The assigned dose by visit will be summarized using mean, standard deviation, minimum, P25, median, P75, and maximum by treatment group.

The assigned dose by visit will also be summarized by treatment group using the number and percentage of subjects assigned to each dose level. Stacked bar graphs displaying assigned dose at all scheduled visits starting with Day 1 will be provided by treatment group.

The median assigned dose by treatment and visit will be displayed graphically for each scheduled study visit using a line plot. The line plot of median assigned dose along with the first and the third quartiles by time will include vertical reference lines to identify the EP as well as the number of subjects by treatment group contributing to each median value.

The following summaries of dose adjustments will be produced twice – the first time counting all dose adjustments, including adjustments related to periods of dose holds (i.e., IRT assignment of a 0-dose), the second time excluding dose adjustments related to periods of dose hold.

The number and percentage of patients with 0, 1, 2..., 10, or >10 dose adjustments will be summarized by treatment group. Summaries will be presented for the following categories of time: Day 1 - < Week 28, Week 28 - <Week 52, and Day 1 - < end of treatment.

The number of dose adjustments per subject will be summarized using mean, standard deviation, minimum, P25, median, P75, and maximum by treatment group. Summaries will be presented for the following categories of time: Day $1 - \langle$ Week 28, Week 28 - \langle Week 52, and Day $1 - \langle$ end of treatment. For the period of time from Day $1 - \langle$ end of treatment, the number of dose adjustments per year will be summarized as well.

The time (in days) that study treatment was withheld for Hgb values ≥ 12 g/dL per subject will be summarized for all subjects and for subjects who had a dose hold using mean, standard deviation, minimum, P25, median, P75, and maximum by treatment group. Summaries will be presented for the following categories of time: Day 1 – < Week 28, Week 28 – <Week 52, Day 1 – < end of treatment, Week 28 - < end of treatment.

Summary tables for the dose adjustment scheme endpoints will also be repeated for the following subgroups (see Section 10.10.1 for subgroup definitions):

- rhEPO hyporesponders (primary definition)
- Region
- Race group
- Dialysis type at randomization
- Baseline weight quartiles

The median most recent dose by treatment and visit will be displayed graphically for each scheduled study visit using a line plot. The line plot of median most recent dose along with the first and the third quartiles by time will include vertical reference lines to identify the EP as well as the number of subjects by treatment group contributing to each median value. This plot will be created by treatment group separately for subjects receiving epoetin alfa and darbepoetin alfa and these plots will also be overlaid on a graph of corresponding Hgb values by visit.

Protocol Amendment 3 updated the dosing algorithm used to assign doses of randomized treatment to subjects in both treatment arms. In order to assess the impact of the dosing algorithm update, Hgb profiles will be created by dosing algorithm category (original algorithm, updated algorithm) and by treatment group. Subjects who were randomized under the original algorithm but switched to the updated algorithm will only have their original dosing algorithm Hgb values included. Hgb values from subjects who were randomized under the updated algorithm will be included in the updated algorithm group (see Section 10.6.3). Only evaluable Hgb values will be used.

Evaluable Hgb data will be fit in an MMRM model with an unstructured covariance matrix using the Kenward-Roger option for PROC MIXED in SAS to estimate denominator degrees of freedom and standard errors. The model will adjust for dialysis type, region, baseline Hgb, baseline Hgb by time, and algorithm by treatment by time. The model will be run without main effects (treatment, time, and algorithm) and without two-way interaction terms (algorithm by time, treatment by time, and algorithm by treatment) for computational ease since in SAS, the main effects and two-way interaction terms are included within the three-way interaction term, thus giving equivalent results. In the event of model convergence issues, the steps outlined in Section 10.10.1 will be followed.

A summary of adjusted mean evaluable Hgb values, standard errors, 95% confidence intervals, and 95% predictions intervals (see Section 10.6.3) for each scheduled study

visit will be provided for each algorithm (original, updated) overall and by treatment group. A corresponding figure will plot the adjusted mean Hgb values in a line plot and the 95% confidence intervals and 95% prediction intervals with shaded regions for each visit for each algorithm group by treatment (including overall), as long as the algorithm/treatment group combination contains at least 20 subjects at the visit.

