 To compare daprodustat to rhE the symptom severity and chan 	PO on • Change from Baseline at Wk 8,12, 28, 52 in PGI-S
Exploratory Objectives	Exploratory Endpoints (statistical testing not planned)
 To further compare daprodustation rhEPO on Hgb variability 	 Hgb observed and change from baseline across all visits to end of treatment % of time Hgb is above, within and below the range of

Objectives	Endpoints
Objectives	 Endpoints 10-11.5 g/dL during EP and MP Number (%) of subjects with mean Hgb above, within and below the Hgb analysis range during EP and at the end of treatment Number (%) of subjects with a Hgb <7.5 g/dL during the EP and MP Number of times Hgb < 7.5 g/dL during the EP and MP Number (%) of subjects with a >1g/dL increase in Hgb over 2 weeks (assessed at Week 2 and Week 4) or a >2 g/dL increase in Hgb within any 4 week period from Week 4 to Week 52 Number (%) of subjects with a >1g/dL decrease in Hgb over 2 weeks (assessed at Week 2 and Week 4) or a >2 g/dL decrease in Hgb within any 4 week period from Week 4 to Week 52 Number (%) of subjects with a >1g/dL decrease in Hgb over 2 weeks (assessed at Week 2 and Week 4) or a >2 g/dL decrease in Hgb within any 4 week period from Week 4 to Week 52 N (%) of subjects with a Hgb value ≥ 12 g/dL during the EP and MP Number of times Hgb ≥ 12 g/dL during the EP and MP
To compare daprodustat to rhEPO on measures of iron parameters	 % of time Hgb ≥ 12 g/dL during the EP and MP Observed and change from baseline in hepcidin, ferritin, TSAT, total iron, TIBC across all visits to end of treatment Average quarterly ferritin Average quarterly TSAT Average quarterly IV iron dose/subject N (%) of subject who met iron management criteria N (%) of subjects who reduced IV iron supplementation relative to baseline (defined as total iron (mg) over 4 weeks prior to randomization) during EP (defined as average monthly IV iron dose (mg) over Weeks 28 to 52)
To further compare daprodustat to rhEPO on BP and BP medication changes	 Observed and change from baseline in SBP, DBP and MAP by visit Number of BP medications per subject by visit Change from baseline in the number of BP medications per subject by visit N (%) of subjects who had no change, an increase or a decrease in the dosage or number of BP medications from baseline by visit

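### The HemoCue table of haemoglobin falls uses a >2 g/dL rise as its second criterion, contradicting the endpoint it is meant to report

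*SAP*

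**What the plan says.** The SAP describes this endpoint in three places.

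- **Section 2.2, exploratory endpoints.** The qualifying event is "a >1g/dL decrease in Hgb over 2 weeks (assessed at Week 2 and Week 4) or a >2 g/dL decrease in Hgb". The second part is assessed over 4-week windows between Weeks 4 and 52. Both parts are falls.
- **Section 8.1.3.1, Table 8.** The row for the endpoint has the same second part: "or a >2 g/dL decrease in Hgb within any 4 week period from Week 4 to Week 52".
- **Section 8.1.3.2, Hgb Variability.** This section turns the endpoint into displays. The HemoCue paragraph covers "subjects with a >1 g/dL decrease in Hgb over 2 weeks (assessed at Week 2 and Week 4) or a >2 g/dL increase". The second criterion uses the same 4-week windows, and evaluable values are tabulated per arm at each visit, with an overall row at Week 52. The first part is a fall and the second is a rise.

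The next paragraph of Section 8.1.3.2 gives the central laboratory version: "The number and percentage of subjects with a >2 g/dL decrease in Hgb within any 4week period". It says of that version: "The central laboratory summary will be considered the primary summary of this data".

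**The concern.** Section 8.1.3.2 is the text a programmer works from; Section 2.2 and Table 8 only name the endpoint. The operative rule therefore carries the wrong direction in half of its definition. Taken literally, a subject whose HemoCue value rises by more than 2 g/dL in 4 weeks is counted as having had a fall. A subject whose only qualifying event is a 4-week fall of more than 2 g/dL is not counted.

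The table describes haemoglobin stability after subjects switch from their prior ESA. If one arm overshoots more than the other, the overall row could show that arm with more falls when what differs is the number of rises. Independent double programming would not necessarily catch this, because both programmers would follow the same specification.

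**Working it through.** The SAP gives no figure to reproduce, so the check compares wording and then counts the affected rows.

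**Step 1: the four parallel paragraphs in Section 8.1.3.2.**

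| Display | 2-week criterion (Weeks 2 and 4) | 4-week criterion (Week 4 to Week 52) |
|---|---|---|
| HemoCue, increase | >1 g/dL increase | >2 g/dL increase |
| Central laboratory, increase | none | >2 g/dL increase |
| HemoCue, decrease | >1 g/dL decrease | **>2 g/dL increase** |
| Central laboratory, decrease | none | >2 g/dL decrease |

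Three rows keep one direction throughout. Only the HemoCue decrease row mixes them, and its 4-week criterion is the one already used two paragraphs earlier in the display that begins "The number and percentage of subjects with a >1 g/dL increase in Hgb over 2 weeks (assessed at Week 2 and Week 4". Nothing in the SAP defines or motivates a combined fall-or-rise endpoint. A copy from the increase paragraph is the likely cause.

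**Step 2: which visits are affected.** The schedule of assessments (Section 10.2.1.1) has post-baseline Year 1 visits at Week 2 and then every 4 weeks from Week 4 to Week 52.

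- Weeks 4 to 52 in 4-week steps: (52 − 4)/4 + 1 = 13 visits. Adding Week 2 gives 14.
- Weeks 8 to 52 in 4-week steps: (52 − 8)/4 + 1 = 12 visits.

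The 2-week criterion applies only at Weeks 2 and 4. At the 12 visits from Week 8 onward only the 4-week criterion operates. The decrease table and the HemoCue increase table would then apply the same rule to the same evaluable HemoCue values and give identical counts. No fall would be recorded at any of these visits.

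**Step 3: Week 4.** Section 8.1.3.2 does not say whether the first 4-week comparison is baseline to Week 4 or Week 4 to Week 8. The clopidogrel analyses in Section 8.2.9 summarise baseline users at Week 4 in a central laboratory table that has only the 4-week criterion, which suggests that Week 4 is assessed. If so, the Week 4 row of the HemoCue decrease table would mix 2-week falls with 4-week rises. Affected visit rows then number 12 (Week 4 not assessed) or 13 (Week 4 assessed) of 14. The overall row at Week 52 is affected on either reading.

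**Step 4: what other displays recover.** The central laboratory decrease table covers 4-week falls correctly. It cannot cover 2-week falls at Week 2, because Section 8.2.9 states that only HemoCue values exist then and the schedule lists no haematology sample at that visit. The HemoCue table is therefore the only display planned for the complete endpoint of Section 2.2, and as written it does not deliver that endpoint.

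**The case against.** The strongest reply is that this is a slip the SAP resolves by itself. The endpoint definition, Table 8 and the next paragraph all say decrease, so only one reading is plausible. The endpoint also ranks low: Section 2.2 lists it under "Exploratory Endpoints (statistical testing not planned"), and the central laboratory summary is primary. Early falls are still specified correctly in the 2-week part of the same paragraph. Later 4-week falls are counted in the central laboratory table, because central laboratory haemoglobin is scheduled at every visit from Week 4 to Week 52. Rows identical to the increase table would probably be noticed before anyone drew a conclusion from them.

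Most of this stands as a limit on importance. No co-primary or principal secondary result is touched, and the two components of the endpoint can be pieced together from unaffected output. It does not make the paragraph right. The specification contradicts the definition it implements, the HemoCue count of 4-week falls is lost, and the overall row for the complete endpoint has no clean substitute. That a reader could guess the intention, or that a later check might expose the error, is no reason to leave it in place.

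A fair point about the count is that Week 4 may also be assessed against the 4-week criterion. That would widen the effect, and the 12 visits from Week 8 to Week 52 are wrong on either reading.

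**Conclusion.** The concern holds. The HemoCue decrease paragraph of Section 8.1.3.2 contradicts Section 2.2, Table 8 and its own central laboratory counterpart. If followed literally, 12 of the 14 scheduled post-baseline Year 1 visits would report rises under a heading of falls (13 affected if Week 4 is also assessed on the 4-week rule), and the overall row would combine both directions. These counts assume the scheduled visits in Section 10.2.1.1 and literal programming of the paragraph. The size of any distortion between arms depends on how often large rises and falls occur, which the SAP does not give.

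The consequence is confined to one exploratory, untested, non-primary table. It should be corrected because that table alone reports the full endpoint; it does not threaten the trial's main conclusions.

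**What to change.** In the HemoCue decrease paragraph of Section 8.1.3.2, change the second criterion from a >2 g/dL increase to a >2 g/dL decrease within any 4-week period from Week 4 to Week 52, so that it agrees with Section 2.2 and Table 8. Check the display program and its validation copy against the corrected text. While the paragraph is open, it would help to state whether Week 4 is the first visit assessed on the 4-week criterion.

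The cost is one word in the SAP and one program check. No data collection, sample size or tested hypothesis changes.
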